#### **STUDY VISIT 1:**

Prior to any tests, it will be ensured that all parents/CYP understand all the information provided and have electronically signed the informed consent form.

Participants will be given the Hailie® sensor and shown how to use this, as described above. Participants will be assessed and given guidance on their inhaler technique and will be provided with an Asthma UK children's asthma plan (unless already in receipt of an asthma plan, see appendix for plan) which will be conducted by a clinical research nurse.

The following information will be collected from all CYP; demographics, asthma history, asthma adherence (measured by self-report, MARS-A), asthma control (measured by ACT questionnaire, FENO – which will be measured by the child breathing out slowly though a mouthpiece where the nitric oxide from the breath will be measured the sensor and computer) and behavioural/psychological data (measured by BMQ, B-IPQ, SRBAI, TSRQ-adapted for this study).

Participants will be randomly assigned to either the 1) control group (n=25) or to the 2) financial incentives-based intervention group (n=25). Participants will be told which group they have been randomly assigned to during this visit.

#### 1. Control group (n=25):

Participants will receive their usual care plus electronic reminders. Participants will not be required to do anything additional as part of this group.

#### 2. Financial incentives-based intervention (n=25):

Participants will be provided with a summary information sheet regarding the intervention programme and will be given the time to read through this and to ask any questions.

Participants will receive gain-framed financial incentives based upon frequency of ICS adherence (£1 per morning dose and £1 per evening dose / maximum £2 per day regardless of prescription / £168 maximum per participant during the 12-week period). Participants will not be able to earn more money by taking their inhaler more than

Research Governance and Integrity Team

prescribed. Participants will be able to see how much money they have earned in real-time by an in-app totaliser which increases by £1 every time the EMD recognises the morning or evening dose has been taken when the Hailie® sensor and the app are synced. Participants will receive their money (in form of an 'One4all' voucher) in 4-weekly instalments (at 4weeks, 8-weeks, and 12-weeks / total £56 per each 4-week period). The 'One4all' voucher will be sent to the child's smartphone via text message. Participants will receive regular messages updating them on their progress in terms of financial incentives. Messages will be delivered as notifications via the app and will be seen on participants' smartphones. Participants will also be able to monitor their adherence in an in-app calendar that follows a traffic-light coding system to display daily adherence (e.g., red if no doses taken, orange if some taken and green if all inhaler puffs are taken per day).

During this intervention period, participant's Hailie® adherence data will also be downloaded and viewed via the Hailie® web portal virtually by the study coordinator at 4-weeks and 8-weeks (in addition to being downloaded at 12-weeks, study visit 2 and 24-weeks, study visit 3) to assess reward amount given.

#### **STUDY VISIT 2:**

The following information will be collected from all participants; asthma history, asthma control (ACT questionnaire, FENO), asthma adherence (self-report, MARS-A and electronically from Hailie®) and behavioural/psychological data (BMQ, B-IPQ, SRBAI, TSRQ-adapted). All participant's Hailie® adherence data will also be downloaded.

1. Control group (n=25):

Participants will continue to receive their usual care plus the electronic reminders. Participants will not be required to do anything additional.

#### 2. Financial incentives-based intervention (n=25):

Participants will receive their final instalment of financial incentives and the financial incentives-based intervention will stop. Participants will no longer receive any financial incentives/rewards and will no longer have access to the in-app totaliser, the weekly messages, and the in-app traffic light calendar. Participants will continue to use their Hailie® device (with the programmed reminders) for the remaining 12-weeks of the study.

#### **STUDY VISIT 3:**

The following information will be collected from all participants; asthma history, asthma control (ACT questionnaire, FENO) asthma adherence (self-report, MARS and electronic from Hailie) and behavioural/psychological data (BMQ, B-IPQ, SRBAI, TSRQ-adapted). All participant's Hailie® adherence data will also be downloaded.

Participants will be asked to return their Hailie® device and will no longer be required to monitor their adherence.

Participants will be invited to take part in a focus group discussion (which will either be inperson at the CCRF or virtually via Microsoft teams) to discuss their perceptions of the trial and to obtain feedback. Focus groups will be optional for participants. Parents/guardians will also be invited to an optional interview to their feedback of the trial.

#### 3.1. STUDY OUTCOME MEASURES

Primary outcome:

• ICS adherence (measured by EMD record of inhaler actuation%)

Secondary outcome:

- Proportion of participants achieving good asthma adherence (≥80%)
- Time to next asthma exacerbation needing a course of oral corticosteroids (OCS)
- Total number of severe exacerbations (incident rate ratio)
- Asthma control (measured by asthma control test (ACT))
- FENO
- Habit (measured by Self-Report Behavioural Automaticity Index, SRBAI)
- Belief in Medicines Questionnaire (BMQ)
- Brief Illness Perception Questionnaire (B-IPQ)
- Autonomous/controlled motivation (adapted from the Treatment Self-Regulation Questionnaire, TSRQ)
- Self-report adherence (Medication Adherence Report Scale for Asthma, MARS-A)

### 4. PARTICIPANT ENTRY

#### 4.1. PRE-REGISTRATION EVALUATIONS

Participants must be contactable by telephone/email and able to receive written information. No pre-registration tests are required.

Prior to any study procedures, informed consent from the parent/guardian and assent from the child or young person will be obtained. The child and their parent/guardian will be given

adequate time to decide whether or not they wish to participate. The child and their parent/guardian should understand that their refusal to participate in the study will not affect their subsequent medical care and if they do consent, they may withdraw at any point without affecting their care. For parents and guardians participating in the subsequent interviews, they are free to withdraw at any time and without giving a reason before the interview. Otherwise, all data will be kept once collected as it will be anonymous.

#### 4.2. INCLUSION CRITERIA

Inclusion criteria are:

- Informed consent obtained from parent/guardian and assent from the child.
- Children or young person with doctor diagnosed asthma presenting to Emergency Departments (ED) with a severe asthma exacerbation (as defined by ERS/ATS guidelines).
- Aged between 11 and 17 years old
- Prescribed maintenance inhaled corticosteroids (ICS) (which can include maintenance and reliever therapy (MART)) for at least 6-months.
- Own their own mobile smartphone (running Android 8 or higher, or iOS 13 or higher)
- Prescribed the following inhalers:
  - o Clenil
  - o Flixotide
  - Symbicort
  - $\circ$  Seretide

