#### 1.2. RATIONALE FOR CURRENT STUDY

In paediatric asthma, there are currently no randomised trials that explore the effectiveness of using financial incentives for improving medication adherence. A US proof-of-concept study that used electronic reminders coupled with financial incentives improved adherence to asthma medications in 12 African American adolescents. Participants were provided with a smartphone and an EMD (with associated App) to provide visual reminders, positive reinforcement (e.g., shooting a basket game and positive text messages when dose is taken) plus rewards (short-term: accessories to decorate personal app avatar and long-term: 1\$ per inhaler dose). Both adherence and asthma control (measured by the asthma control test ACT) improved across the 8-week period.

Similarly, a feasibility study conducted by ourselves found the use of financial incentives to be feasible and acceptable for improving adherence in paediatric asthma. Adolescents diagnosed with asthma, who had poor medication adherence (<80%) and poor asthma control were recruited from an outpatient asthma clinic. Twelve adolescents were invited to take part and 10 were recruited (7 males, 3 females, 12-16 years) to a 24-week intervention that consisted of eight weeks of electronic reminders and financial incentives related to their adherence (£1 per morning dosage, £1 per evening dosage, capped at £2 per day). Eight out of 10 adolescents provided adherence measurements up to the final study visit. Three adolescents successfully paired their mobile app and EMD up to the final study visit which was associated with improved adherence. The 7 adolescents unable to pair their mobile app and EMD had no change in adherence. Overall, adherence did not significantly change. Exit interviews with adolescents revealed reminders and incentives were welcomed but issues with the technology was frustrating. Adolescents also commented that the intervention was useful by promoting self-monitoring and increasing motivation to take medication.

These findings within asthma warrant the further exploration of this intervention design using financial incentives with the inclusion of a larger sample size and randomisation. In addition, to explore the potential mediators of sustained behaviour change, motivation and the key feature of habit, automaticity, will be tracked in this study.

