All CYP will be required to download the Hailie® associated app on their smartphones and to sync their Hailie® sensor with the associated app, via Bluetooth. The Hailie® sensor will detect medication usage from the attached preventer inhaler and send this to the Hailie® associated app on the CYP's smartphone, also via Bluetooth. The Hailie® associated app will then automatically upload (via WIFI/data connection) the medication usage data to the secure cloud-based Hailie® web portal where the research team will be able to view the data (see image below).

Wi-Fi connection

All CYP will regularly charge and sync their Hailie® device to ensure all data are collected accurately, they will be prompted to do this throughout the study through app notifications. Parents/guardians/CYP will be asked to inform a member of the study team if there are any issues with their EMDs so this can be sorted as soon as possible.

All CYP's Hailie® devices or smartphones will be programmed with both morning and evening audio-visual reminders across the 24-week period. CYP will choose the time of their reminders which will be recorded by the researcher.

There will be no covert adherence monitoring and CYP's adherence data will be downloaded and viewed by the study coordinator before/at each study visit (study visit 2, 12-weeks and study visit 3, 24-weeks). For those in the intervention group, adherence data will also be downloaded and viewed at 4-weeks, 8-weeks to calculate reward amount given only.

At the end of the 24-week programme, all participants will be invited to join a focus group discussion (which will either be in-person at the CCRF or virtually via Microsoft teams) with other CYP from the study. There will be up to 10 participants per focus group and numbers will be dependent upon participant availability. Focus groups with participants from the intervention group and with participants from the control group will be conducted separately. Focus groups will be optional for participants. Parents/guardians will also be invited to take part in an interview in person / via email or telephone to obtain their feedback about the programme. These interviews will be optional and will last approximately 45minutes.

Research Governance and Integrity Team

Interviews will be conducted at study visit 3 and will be conducted in person or virtually (via telephone or via Microsoft Teams, dependent upon preference).

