#### 7.2 Statistical methods and sample size

As this is a pilot study, a formal sample size calculation is not required. However, the estimated sample size of 50 participants in total is based upon a calculation from unpublished adherence data obtained from Royal Brompton Hospital from 400 children. Mean adherence in the sample was 65% (SD 22%). A Cochrane review of adherence interventions to ICS for asthma found that electronic trackers or reminders led to better adherence of 19% (95% CI 14.47 to 25.26). Based upon this information, to give 80% power to achieve a 19% difference between the intervention group and controls, 21 participants are required per group. The target of 25 per group accounts for participant dropout. This is supported by evidence that as a pilot study, 25 participants per group, with a total of 50 participants is sufficient.

Data analysis will be conducted using the Statistical Package for the Social Services (SPSS). Statistical analysis of quantitative, normally distributed data will be reported with means ± standard deviations (SD) and non-parametric data will be reported as medians with interquartile range. Data will be tested for normality using visual inspection, histograms, and Kolmogorov-Smirnov testing. Parametric tests will be used where possible for normally distributed data and logarithmically transformed data, otherwise appropriate non-parametric tests shall be used. The significance levels for all tests will be set at <0.5.

Categorical data will be reported as proportions. Comparative analysis of variance between 2 groups for continuous data will be performed using the student's t test for normally distributed data and the Mann Whitney U tests for non-normally distributed data and for more than 2 groups the ANOVA or Kruskal Wallis respectively. A comparison of the proportions between groups will be performed using the Pearson Chi 2 tests. Within group analysis the ANOVA test will also be used.

Questionnaire data will be used alongside group comparisons to observe any notable changes or differences between groups.

Qualitative data obtained from the focus groups will be thematically analysed. An independent researcher will aid with the facilitation/analysis of qualitative aspect of the study to ensure there is no bias.

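### Nothing confirms that app and sensor pair before a child is randomised, although the described routes for the primary outcome and the incentive both depend on syncing

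*Combined protocol and SAP*

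**What the plan says.** **Entry.** Section 4.2 requires that the child "Own their own mobile smartphone (running Android 8 or higher, or iOS 13 or higher". It also lists four products under "Prescribed the following inhalers", without giving a reason for the list. Section 4.1 states: "No pre-registration tests are required". No criterion in 4.2 or 4.3 mentions pairing.

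**Use of the technology.** Section 3 says: "All CYP will be required to download the Hailie® associated app on their smartphones and to sync their Hailie® sensor with the associated app". The sensor passes usage data to the app by Bluetooth, and the app uploads them to the web portal, where the team views them. No other read-out is described, including at visit 3, when the sensor is returned. In the intervention arm the in-app totaliser rises when sensor and app are synced, and the reward is worked out from portal downloads.

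**Visit 1.** The sensor is handed over and demonstrated. Both the visit 1 text and the section 6 schedule list this before randomisation. Visits may be remote.

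**Earlier experience (section 1.2).** Of the minority whose technology worked, the section reports: "Three adolescents successfully paired their mobile app and EMD up to the final study visit which was associated with improved adherence". Its account of the remainder is less favourable: "The 7 adolescents unable to pair their mobile app and EMD had no change in adherence". On how many supplied outcome data, it says: "Eight out of 10 adolescents provided adherence measurements up to the final study visit".

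**Sample size (section 7.2).** 21 per group for a 19-point difference with SD 22 and 80% power. Then: "The target of 25 per group accounts for participant dropout".

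**The concern.** The sponsor's own small study points to pairing as the weak link, yet the new trial sets only a phone specification and an inhaler list. Neither shows that a given phone and sensor work together. Pairing is an instruction to participants after entry, not a condition of entry or allocation.

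Two things are at stake. An unpaired child in either arm may have no primary outcome. An unpaired child in the intervention arm does not see earnings accrue, and the plan describes no other way to credit them, so that child is analysed as treated without receiving the incentive. The second effect pulls the estimated difference towards zero, and Aim 3 uses that estimate to plan a definitive trial.

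Detection also differs by arm. Intervention data are viewed at 4 and 8 weeks, but control data are not scheduled to be viewed until around week 12. A failed pairing could go unseen for longer among controls.

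**Working it through.** **Inputs.** From section 7.2: SD 22 points, difference 19 points, power 80%, 21 per group raised to 25. From section 1.2: of 10 adolescents, 3 paired to the final visit, 7 unable to pair, 8 supplying adherence data. Assumed: two-sided alpha of 0.05. The plan prints <0.5, but that would give only about 7 per group (6.16 rounded up), whereas 0.05 reproduces the stated 21.

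**1. The plan's own figure.** n per group = 2 × [22 × (1.960 + 0.842) / 19]² = 21.05. This agrees with 21 (22 if rounded up, 23 with a t-test). The implied loss allowance is (25 − 21)/25 = 16%.

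**2. What the feasibility study says about outcome loss.** Eight supplied data and at most three of these were paired, so at least 8 − 3 = 5 of the 7 unpaired adolescents supplied data. Documented outcome loss is 2/10 = 20%, not 7/10. Applied here, 25 × 0.80 = 20 per arm. The standard error is 22 × √(2/20) = 6.96, and power = Φ(19/6.96 − 1.96) = 78%, against 80% at 21 per arm. That shortfall is small.

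**3. Dilution.** Suppose all 25 per arm are measured, paired children gain the full 19 points, and a fraction f of the intervention arm is unpaired and gains nothing. The expected difference is 19 × (1 − f). The standard error is 22 × √(2/25) = 6.22, and power = Φ(difference/6.22 − 1.96).

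| Unpaired, f | Expected difference | Power, 25 per arm |
|---|---|---|
| 0 | 19.0 | 86% |
| 10% | 17.1 | 78% |
| 20% | 15.2 | 69% |
| 40% | 11.4 | 45% |
| 70% (feasibility proportion) | 5.7 | 15% |

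These use the normal approximation; t-test power is at most about 2 percentage points lower. The 10% to 40% range is an assumption. The last row is a reference point, not a forecast: 7 of 10 has an exact 95% interval of 35% to 93%.

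**The case against.** A reader might infer that children who cannot pair will be randomised and will certainly have no primary outcome, or that some 70% of outcomes will be lost. The documents do not support this. At least 5 of the 7 unpaired adolescents supplied adherence data. How those data were retrieved is not stated, so neither certain loss nor a working fallback can be assumed. Section 1.2 does not say whether phones, app or sensor were the same as those planned now. Nor does anything in the plan exclude unpaired children after randomisation; section 4.4 keeps data already collected.

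Other objections carry weight:

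- Section 1.2 measures success as pairing up to the final visit and does not say whether the seven failed at set-up or later. A visit 1 check catches only the former.
- The demonstration, the app prompts to charge and sync, and the request to report faults may all lower the failure rate. None of them confirms pairing before allocation.
- Better adherence among the three who paired is an association, so zero gain in unpaired children is an assumption.
- The trial is a pilot, which section 7.2 says needs no formal sample size, and Aim 2 is feasibility. Randomising children with ordinary phones and watching what fails is informative. A log keeps the count of failures but not those children's outcomes.

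These points limit the size of the concern. They do not supply the missing step.

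**Conclusion.** The gap is real: pairing is needed both to transmit the outcome and to deliver the incentive as described, it was reported to fail in 7 of 10 adolescents, and nothing verifies it before allocation. A child who cannot pair can be randomised, and the plan has no rule for that child.

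The only documented outcome loss, 20% against an implied 16%, moves power from about 80% to 78%. It is not shown to be caused by pairing. Dilution matters more. The fall from 19 to between 17.1 and 11.4 points, with power between 78% and 45%, rests on the assumed 10% to 40% unpaired, no gain in those children, the full planned effect in the rest, SD 22 and two-sided 0.05. The change is worth making because it is cheap and treats both arms alike, not because a large loss has been demonstrated.

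**What to change.** Add to section 4.2 and to the visit 1 sequence in section 3 a condition for randomisation: app installed, sensor paired, and a test actuation seen on the web portal. Use Sealed Envelope only after this check, including at remote and home visits. Log every child who fails it, with the reason where known, and report the number as a feasibility result under Aim 2.

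The cost is a few minutes at a visit where the sensor is already issued, plus a short amendment. The population narrows slightly, to children for whom the app-based intervention can at least be started. The check does not prevent later loss of pairing, so the protocol should also say how unsynced periods are handled. If the sponsor prefers to randomise children who cannot pair, it should instead specify a fallback for reading the sensor and for crediting the incentive.

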#### 4.3. EXCLUSION CRITERIA

Exclusion criteria are:

- Parent/guardian unable to provide consent / CYP unable to provide assent
- CYP with other, co-existing respiratory conditions
- Parent/guardian/CYP who are not fluent or able to understand the information provided in English
- CYP who are involved in other intervention research studies (including CTIMPs)

#### 4.4. WITHDRAWAL CRITERIA

CYP will be withdrawn from the study if CYP/parent/guardian refuse or withdraw their consent to participate in the study. Parent/guardian/CYP can refuse intervention, adherence monitoring or any study tests/questionnaires at any time without any negative consequences. Participation or withdrawal in the study will not affect the patient's clinical care and participants will not be prevented from receiving any treatment that may be required without participating in the study.

We don't anticipate any reason to stop the trial or other research early.

Any data already collected from a participant who decides to withdraw from the study will be kept. If a participant decides to withdraw from the study, data already collected until that point in the study will be used.

### **5. ADVERSE EVENTS**

#### 5.1. **DEFINITIONS**

Adverse Event (AE): any untoward medical occurrence in a patient or clinical study subject.

Serious Adverse Event (SAE): any untoward and unexpected medical occurrence or effect that:

- Results in death
- Is life-threatening refers to an event in which the subject was at risk of death at the time of the event; it does not refer to an event which hypothetically might have caused death if it were more severe
- Requires hospitalisation, or prolongation of existing inpatients' hospitalisation
- · Results in persistent or significant disability or incapacity
- Is a congenital anomaly or birth defect

Medical judgement should be exercised in deciding whether an AE is serious in other situations. Important AEs that are not immediately life-threatening or do not result in death or hospitalisation but may jeopardise the subject or may require intervention to prevent one of the other outcomes listed in the definition above, should also be considered serious.

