#### 5.2. **REPORTING PROCEDURES**

All adverse events should be reported. Depending on the nature of the event the reporting procedures below should be followed. Any questions concerning adverse event reporting should be directed to the Chief Investigator in the first instance.

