#### 5.3.1 Non serious AEs

All such events, whether expected or not, should be recorded- it should be specified if only some non-serious AEs will be recorded, any reporting should be consistent with the purpose of the trial end points.

Potential AEs and known complications:

Procedure	Known complications
n/a	n/a

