#### 5.3.2 Serious AEs

An SAE form should be completed and emailed to the Chief Investigator within 24 hours. However, relapse and death due to asthma and hospitalisations for elective treatment of a pre-existing condition do not need reporting as SAEs.

All SAEs should be reported to the London-Bloomsbury REC where in the opinion of the Chief Investigator, the event was:

- 'related', ie resulted from the administration of any of the research procedures; and
- 'unexpected', ie an event that is not listed in the protocol as an expected occurrence

Reports of related and unexpected SAEs should be submitted within 15 days of the Chief Investigator becoming aware of the event, using the NRES SAE form for non-IMP studies. The Chief Investigator must also notify the Sponsor of all related and unexpected SAEs.

Local investigators should report any SAEs as required by their Local Research Ethics Committee, Sponsor and/or Research & Development Office.

Contact details for reporting SAEs [contact] CI email (and contact details below) Please send SAE forms to: [name] [contact] [name] / Email: [contact] (Mon to Fri 09.00 – 17.00)

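### Section 5.1 makes unexpectedness part of the SAE definition, while section 5.3.2 treats it as a later judgement by the Chief Investigator on events that are already SAEs; the two need reconciling.

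*Combined protocol and SAP*

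**What the plan says.** Section 5.1 gives two definitions in succession. An adverse event is "any untoward medical occurrence in a patient or clinical study subject", with no condition on expectedness. A serious adverse event is "any untoward and unexpected medical occurrence or effect that" meets one of the listed criteria (death, threat to life, hospitalisation and so on). A closing paragraph adds: "Medical judgement should be exercised in deciding whether an AE is serious in other situations".

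Section 5.2 asks for every adverse event to be reported and then directs the reader onward: "Depending on the nature of the event the reporting procedures below should be followed". Two procedures follow.

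- Section 5.3.1, for non-serious events: "All such events, whether expected or not, should be recorded". Its table, introduced as "Potential AEs and known complications", contains only n/a.
- Section 5.3.2, for serious events: "An SAE form should be completed and emailed to the Chief Investigator within 24 hours". Asthma relapse, death from asthma and elective admissions for a pre-existing condition are exempted from SAE reporting. The Chief Investigator then decides which SAEs were both related and unexpected, and those go to the REC and the sponsor. Here, and not in 5.1, unexpected is explained: "ie an event that is not listed in the protocol as an expected occurrence".

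**The concern.** Seriousness and expectedness are separate questions, and 5.3.2 keeps them separate: seriousness triggers the form, and expectedness helps decide onward reporting. Section 5.1 merges them, so expectedness is applied twice. The first time is at the point of definition, where the protocol names no assessor and requires no form. The second is by the Chief Investigator.

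Three things are at stake for a serious event that someone regards as expected at first sight: prompt notice to the Chief Investigator, the Chief Investigator's own judgement of relatedness and expectedness, and a complete count of serious events. One aim of this pilot is to inform a definitive trial, so an ambiguous definition could also be carried forward.

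**Working it through.** No rate, variance or sample size enters this point, so there is nothing to calculate. The check is to follow one event through section 5 under each available meaning of unexpected. Take a serious event, such as a non-elective hospital admission, that is not covered by the exemptions in 5.3.2.

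**Reading A: unexpected has its ordinary meaning, and the person who first sees the event regards it as expected.**

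1. Section 5.1: the event meets a seriousness criterion but is not unexpected, so it is not an SAE.
2. Section 5.1, closing paragraph: this extends seriousness to situations outside the listed criteria. It does not remove the word unexpected for an event that meets a listed criterion, so it does not restore the event.
3. Section 5.3.2: the 24-hour form is for SAEs, so none is required. The Chief Investigator's test also starts from SAEs, so it is not reached.
4. Section 5.3.1: the wording that includes expected events stands under the heading for non-serious events, and this event is serious.
5. Section 5.2: the general instruction to report still applies, but it points to the two procedures above and neither fits. No form, deadline or assessor is specified.

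**Reading B: unexpected has the meaning given in 5.3.2, that is, not listed in the protocol as expected.**

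1. The table in 5.3.1 lists nothing. The only other candidates for a list are the exemptions in 5.3.2, which are outside SAE reporting in any case.
2. The event is therefore unexpected, satisfies 5.1, and goes on the 24-hour form. Almost nothing is lost.
3. But every SAE is now unexpected by definition, so the expectedness half of the test in 5.3.2 can never exclude anything.

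| | Reading A | Reading B |
|---|---|---|
| SAE under 5.1? | No | Yes |
| 24-hour form? | No | Yes |
| Chief Investigator's test reached? | No | Yes, but its expectedness half is empty |
| Still to be reported under 5.2? | Yes, with no fitting procedure | Yes |

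Under either reading, 5.1 and 5.3.2 do not fit together. The exemptions show which one is out of place: asthma relapse and asthma death would hardly need exempting in this population if expected events were already outside the SAE definition. The structure of 5.3.2 assumes that SAEs include expected events.

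**The case against.** The strongest reply is that the protocol explains unexpected only once, in 5.3.2, and that a careful reader would use that meaning throughout. Since almost nothing is listed, nearly every serious event would then qualify under 5.1. This largely stands, and it limits the size of the point. It does not remove it: 5.1 comes first and contains no cross-reference, so a reader applying the ordinary meaning does not contradict anything in that section. It also follows that the empty table in 5.3.1 narrows the gap; it does not widen it.

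It is also fair to say that an event the Chief Investigator judged expected would not go to the REC under 5.3.2 anyway. That is correct. The loss is the form, the timing and the Chief Investigator's own judgement.

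A reader might infer more than the documents support:

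- *That serious events go unreported.* Section 5.2 requires all adverse events to be reported and sends questions about reporting to the Chief Investigator. The event misses the SAE pathway; it is not excused from reporting.
- *That asthma admissions are lost through this wording.* Relapse and death from asthma are exempted by a separate sentence in 5.3.2. Severe exacerbations, which by the definition in the Study Summary include those leading to hospital admission, are counted as a secondary outcome.
- *That each hospital would apply its own standard, so that SAE counts could not be compared between arms.* Section 3 describes the emergency departments as places of recruitment. Visits are at one facility, remote or at home, and section 7.1 has one study coordinator collecting data. Section 5.3.2 mentions local investigators, but nothing shows departments classifying events independently. Sections 3.1 and 7.2 plan no comparison of SAEs between arms, and open allocation alone does not show that a difference would arise.
- *That a number of missed events can be stated.* The documents give no rate for serious events outside the exemptions.

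**Conclusion.** The contradiction is real and can be verified from section 5 alone. Section 5.1 makes unexpectedness a condition for being an SAE; 5.3.2 makes it a later test on events that already are SAEs. Read literally, 5.1 can keep a serious event that is judged expected off the 24-hour form and away from the Chief Investigator's assessment.

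Its practical size depends on which meaning of unexpected is applied in 5.1. With the meaning from 5.3.2, the gap is close to nil. With the ordinary meaning, it covers whichever non-exempt serious events the first assessor regards as expected. How many that would be among 50 participants followed for 24 weeks cannot be derived from the documents. The conclusion rests on the wording only and assumes no event rate. It is a defect in safety-reporting wording in a behavioural pilot and does not touch the primary outcome, the sample size or the planned analysis. It is worth correcting because the correction is specific and nearly free.

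**What to change.** Delete *and unexpected* from the SAE definition in section 5.1, so that an untoward occurrence meeting a seriousness criterion is an SAE and goes on the form, subject to the exemptions already stated in 5.3.2. Leave expectedness to the Chief Investigator at 5.3.2, where it bears only on onward reporting to the REC and the sponsor.

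Filling in the table in 5.3.1 should not be part of this change. That table concerns known complications of procedures, under non-serious events, and listing events there as expected would narrow what 5.3.2 sends to the REC and the sponsor.

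The cost is a two-word deletion in an amendment and possibly a few more SAE forms in a trial of 50 participants.
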